2. Whole blood NAD+		• Genetic analysis			
3. Serum electrolytes					
(Na, Cl, K)		Urine:			
4. Bicarbonate		• Future biomarkers			
5. Calcium and					
phosphate					
6. Blood glucose					
7. CBC with platelets					
T T •					
Urine:					
1. Urinalysis					
2. Urine creatinine					
3. UACK and UPCK					
4. Urine glucose					
5. Lactate					
0. Urine phosphate					
/. Urine NAD+					
metabolome					

Table 4: Blood and urine tests for research laboratory, safety, and repository

Due to limited direct interactions with the participants, safety assessments will be performed by collection of EHR data, participant interviews, vital sign measurements, physical examination, and laboratory tests, including complete blood count and comprehensive metabolic panel, and diagnostic tests or procedures. Participants' reported symptoms or complaints recorded in the medical record will be reviewed and recorded in the appropriate eCRF. In addition, information will be solicited from the participants and designated staff physicians to supplement accurate and complete safety assessment.

Each participating investigator will have primary responsibility for the safety of the individual participants under his or her care. The investigators will determine daily if any adverse events occur during the period from enrollment through study intervention and will determine if such adverse events are reportable. Thereafter, adverse events will not be required to be reported unless the investigator feels the adverse event was related to the study drug or study procedures.

The site investigator will (i) provide a verbatim term (a diagnosis where possible) for detected and reportable AE, (ii) each AE will also be described in terms of duration (start and stop date), severity, association with the study product, action(s) taken, and outcome, (iii) classify and assign a grade to each detected and reportable adverse event using the CTCAE v. 5.0 classification system, and (iv) rate the likelihood that the event was related to the study drug.

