A team of medical monitors (Safety Adjudication Committee, SAC), composed of three clinicians with expertise in infectious disease or acute care management, one from each study site, independent of the study investigators will review the medical charts for unexpected AE /SAE data weekly during the study intervention period. The senior SAC member will serve as SAC Chair. The SAC will confirm the verbatim term (a diagnosis where possible) for detected and reportable adverse event with knowledge of the study site physician's rating and then classify and assign a grade to each detected and reportable adverse event using the CTCAE v. 5.0 classification system. Disagreements between the study site investigator and the SAC member will be adjudicated weekly on a call facilitated by the SAC Chair.

All AEs will be recorded on the AE eCRF. Verbatim terms for AEs will be coded to the current version of the MedDRA coding dictionary at the DCC. Verbatim terms will be coded at the Lower Level Term (LLT) where possible and to the Preferred Term (PT) otherwise. Accurate mapping to CTCAE will be confirmed during the coding review process. AEs and SAEs will be aggregated and reported for the DSMB at the PT level. If the SAC identifies an unexpected SAE, sIRB and FDA expedited reporting procedures will be followed and the DSMB will be notified.

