8.3.4 TIME PERIOD AND FREQUENCY FOR EVENT ASSESSMENT AND FOLLOW-UP

The study investigators will assess and record all events with start dates occurring any time after informed consent is obtained until Day 90 – the last visit. The study investigator will review EHR daily to collect and assess all AEs (including SAEs) from the time participants provided consent to the study until Day 10 and again during Day 30 and Day 90 follow-up visits regardless of its relationship to study drug. At each visit, the investigator will inquire about the occurrence of any new and the prognosis of already documented AE/SAEs since the last visit. All AEs will be captured in detail and followed to satisfactory resolution or stabilization, until the investigator deems the event chronic or not clinically significant and until the participant is considered to be stable. The participants will receive standard of care for the events. Site investigators will also assess if there is a reasonable possibility that the study drug or procedure caused the event. Investigators will also consider if the event is explained by the participant's underlying medical conditions, anticipated clinical course, previous medical conditions, and concomitant medications.

Routine and safety laboratory values from the respective hospital laboratories will be reported by each site investigator to the SAC as soon as the results are available to the study database. Participants will receive standard of care for the event and followed to satisfactory resolution or stabilization, The DCC will review laboratory results for completeness. Any abnormal laboratory test results (clinical chemistry, hematology, or urinalysis) or other safety assessment (e.g., CPK), including those that worsen from the baseline, felt to be clinically significant in the medical and scientific judgement of the investigator, will be recorded as AEs. The SAC will review AEs weekly and SAEs on a daily basis and any events that the clinical centers categorize as requiring treatment discontinuation for safety reasons.

The following laboratory results will be flagged as expected study AEs in this trial:

- Thrombocytopenia: Platelet count >25% reduction from the baseline;
- Liver function test abnormalities: AST, ALT, total bilirubin, alkaline phosphatase > 4 times the upper limit of normal;
- Creatinine phosphokinase (CPK): > 4 times upper limit of normal;

The following symptoms will be flagged as expected study AEs in this trial:

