8.3.7 EVENT ADJUDICATION PROCESS

Unexpected AEs and SAEs occurring from the time the informed consent signed through the Day 90 visit will be documented, recorded, and reported. Upon entry into REDCap eCRF, a notification will be generated to the independent site SAC member that unexpected AEs are ready for review. SAC members will be expected to review unexpected AEs within one week of notification. (Unexpected SAEs will have different language in the text and will require same day review by the SAC member.) SAC review will be separate from the expedited SAE reporting process and incomplete SAC assessment will in no way delay expedited SAE reporting.

Adjudicators will be blinded to the study treatment actually given to each patient and will use subject matter knowledge to render opinions regarding, for example, relatedness to treatment. The database will be configured so that certain baseline data will be viewable, including age, race, gender, BMI, diabetic status (diabetic, not diabetic), and current smoking status (smoker, not a smoker).

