9.4.6 PLANNED INTERIM ANALYSES

An O'Brien-Fleming procedure will be used to conduct an interim analysis for safety when 50% of the patients complete the study. A statistical basis for stopping the study at the first look will be achieved if the test statistic for the primary safety endpoint (the occurrence of at least one serious adverse event of grade 3 or higher or the occurrence of thrombocytopenia less than 50,000 per microliter) indicates harm in the NR arm at p \leq 0.003. If the test statistic does not reach p \leq 0.003 at the first look then the trial will proceed to the final analysis. The statisticians (Drs. [name] and [name]) will inform the principal investigator if the interim analysis crosses the boundary in the direction of harm is observed (p \leq 0.003). A treatment effect will be declared harmful at the final analysis if the test statistic indicates harm and p \leq 0.047. The safety data will be summarized at interim analysis. The statisticians will inform the DSMB if there are any safety concerns at the interim analysis. Any decision on stopping the study based on safety will be made in coordination with NIDDK and the DSMB.

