Adverse Events and Serious Adverse Events: Reportable AEs will be entered into the REDCap study database. Reportable AEs will be entered, classified, and graded according to the most current versions of the CTCAE by the site investigator and independent site SAC Physician. Adverse events indicated as Serious Adverse Events will result in real-time alerts through the REDCap system to support expedited reporting. Entry of reportable Adverse Events will trigger notification to the independent SAC physician to initiate the independent review and adjudication process as described in section 8.3.7. AEs will be coded at the DCC using the MedDRA controlled terminology.

Biosample Inventory and Tracking: The REDCap study database will include screens at each visit for sites to report samples obtained and shipped to the UTHSA COVID-19 Repository. Sample tracking will trigger notification to the repository. Samples received will be reconciled with REDCap biosample tracking on the day of receipt. Data status reports will flag expected and missing sample tracking data.

Data Status Reports: Enrollment data will be entered into REDCap on the day of enrollment. Enrollment entry enables tracking and management of participant data and samples and will trigger notification to the site and DCC study team. Data entry will be entered every day during the 10-day treatment period and within one week of follow-up visits. Late data will be listed on an exception report by site and by participant. Similarly, data discrepancies will be resolved within a week of firing. Late data discrepancy resolutions will be listed on an exception report by site and by patient. Data will be reviewed by the DCC within 24 hours of complete entry. The site investigator will be responsible for review of data collection tools and processes, and review of data and reports.

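### After the 10-day intervention, section 8.2 limits adverse event reporting to events judged related while sections 8.3.4 and 8.3.7 do not, so Day 11–90 safety data could be incomplete and differ by site

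*Combined protocol and SAP*

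**What the plan says.** Section 8.2 makes the investigator "determine daily if any adverse events occur during the period from enrollment through study intervention" and decide which of those events are reportable. It continues: "Thereafter, adverse events will not be required to be reported unless the investigator feels the adverse event was related to the study drug" or to study procedures.

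Section 8.3.4 sets a different rule: "The study investigators will assess and record all events with start dates occurring any time after informed consent is obtained until Day 90". It adds that AEs and SAEs are collected from consent "until Day 10 and again during Day 30 and Day 90 follow-up visits regardless of its relationship to study drug". Section 8.3.7 states: "Unexpected AEs and SAEs occurring from the time the informed consent signed through the Day 90 visit will be documented, recorded, and reported". The Schedule of Activities marks AE assessment at Day 30 and Day 90.

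The text on what reaches the database is also mixed. A later paragraph of 8.2 says "All AEs will be recorded on the AE eCRF". Section 10.1.8.1 says "Reportable AEs will be entered into the REDCap study database", and 9.4.2 lists reportable AEs.

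The primary safety objective (synopsis and section 3) covers the 10-day intervention period. The endpoint text, the Fisher test in 9.4.2 and the monitoring rule in 9.4.6 give no time window. Section 9.4.6 plans "an interim analysis for safety when 50% of the patients complete the study", and the synopsis has participation lasting up to 90 days.

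**The concern.** Sections 8.2 and 8.3.4 cannot both govern what a site does with a Day 11–90 event that the investigator thinks is unrelated. Under 8.2 the event may go no further. Under 8.3.4 it is recorded.

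Two things are at stake. First, the information on late harm would be filtered by investigator opinion wherever 8.2 is followed. In patients with COVID-19 and AKI, most serious events have a ready alternative explanation, so that filter could remove much of what occurs. Second, 9.4.2 tabulates and tests AEs by clinical site as well as overall. If sites follow different rules, differences in site event rates after Day 10 partly reflect the rule and not the patients.

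**Working it through.** **Step 1: do the sections conflict?** Treatment of an event judged unrelated:

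| Source | Through Day 10 | Day 11–90 |
|---|---|---|
| 8.2, investigator duties | Determined daily; no relatedness filter | Reporting not required |
| 8.3.4 | Assessed and recorded | Assessed and recorded |
| 8.3.7 | Unexpected AEs and SAEs recorded and reported | Same |
| Schedule of Activities | AE assessment daily | AE assessment at Days 30 and 90 |

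The 8.2 sentence is the outlier, and only in the right-hand column. Section 8.3.6 separately exempts listed COVID-19 outcomes from AE reporting unless they may be related. It has no time limit, so it does not distinguish the two rules.

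**Step 2: which event types are exposed after Day 10?**
- Platelet decline: little exposed. Table 4 schedules a CBC with platelets at Days 30 and 90.
- Unexpected SAEs: covered to Day 90 by 8.3.7.
- Expected SAEs and non-serious grade 3–4 AEs: exposed if judged unrelated. The latter matter because 9.4.2 counts grade 3 or 4 AEs, not only SAEs.

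**Step 3: effect on the primary safety count.** If events are counted through Day 10, neither rule filters by relatedness and the difference is 0. If they are counted to Day 90, the rules can differ.

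**Step 4: size under a Day 90 count.** The documents give no power figure or event rates for safety, so there is no plan figure to reproduce and the rates below are assumptions. Let b be the proportion with an event by Day 10, q the proportion of event-free patients with a later event, and r the share of late events judged related.

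- Recorded under 8.3.4: b + (1 − b)q
- Recorded under 8.2: b + (1 − b)qr
- Difference: (1 − b)q(1 − r)

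With q = 10% and r = 0 in both arms:

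| b | 8.2 | 8.3.4 | Difference |
|---|---|---|---|
| 20% | 20% | 28% | 8 points |
| 30% | 30% | 37% | 7 points |
| 40% | 40% | 46% | 6 points |

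With b = 30% and 0, 1, 2 or 3 of three equal-sized sites following 8.3.4, the pooled recorded proportion is 30 + (k/3) × 7 = 30.0, 32.3, 34.7 or 37.0%.

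**Step 5: a late harm, as an illustration.** Keep q = 10% on placebo and assume q = 40% on NR, with equal Day 10 rates. The figures are the exact probability that a two-sided Fisher test reaches p ≤ 0.047 (the final level in 9.4.6) with 50 per arm (100 randomized 1:1). At b = 30%, 8.3.4 records 30 + 70 × 0.40 = 58% versus 30 + 70 × 0.10 = 37%. With r = 0.5, 8.2 records 30 + 70 × 0.20 = 44% versus 30 + 70 × 0.05 = 33.5%.

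| b | 8.3.4, all late events | 8.2, r = 0.5 | 8.2, r = 0 |
|---|---|---|---|
| 20% | 63% | 18% | 2% |
| 30% | 50% | 14% | 3% |
| 40% | 38% | 11% | 3% |

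The r = 0 column is the test's false-positive rate, because the filter has removed the whole late difference.

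**The case against.** **Recording is not reporting.** Section 8.2 speaks of reporting and 8.3.4 of recording, so the text could mean record everything and report only what is related. Other text supports this: 8.3.1 captures all grade 3 and 4 AEs, 8.3.2 puts all SAEs on an SAE eCRF, and 8.2 itself puts all AEs on the AE eCRF. The reading is possible but does not settle the matter. Section 8.2 grades events that are detected and reportable, 10.1.8.1 enters reportable AEs, 9.4.2 lists reportable AEs, and 8.3.7 uses both verbs through Day 90.

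**Sites may not diverge, and the comparison is not biased.** All sites must follow one manual of operations with common data definitions, which is not among these documents. It may resolve the point, though it should not have to choose between two protocol sections. Investigators are blinded and randomization is stratified by site, so under-recording falls on both arms. This part stands: the expected cost is lost information and non-comparable site rates, not a bias favouring one arm.

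**Two stronger readings.** A reader might infer that the primary safety endpoint itself depends on the rule a site follows. The documents do not support that without a condition: the objective names the 10-day period, where the rules agree.

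A reader might also infer that limiting the count to Day 10 sacrifices power. At assumed rates of 15% versus 30% by Day 10, Fisher power is 33%. If the doubling persisted to 30% versus 60% at Day 90, it would be 83%. That compares counting windows, not reporting rules, and nothing in the documents supports a doubling that lasts 80 days after treatment. If the harm ends with treatment, Day 90 is 30% versus 42.4% (30 + 70 × 15/85) or, with 15 points added in each arm, 30% versus 45%. Power is then 19% or 27%, below the Day 10 figure.

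**Conclusion.** The contradiction is real and should be corrected. Following 8.2 would filter Day 11–90 events by investigator opinion, against 8.3.4, 8.3.7 and the Schedule of Activities. The exposed data are mainly expected SAEs and non-serious grade 3–4 AEs judged unrelated.

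For the primary safety count the consequence is conditional. It is zero if events are counted over the 10-day period in the objective. It arises only if later events are counted, which 9.4.2 and 9.4.6 leave open while the interim look waits for patients to complete the study. Under a Day 90 count, the gap of 6 to 8 points and the loss of ability to see a late harm both rest on assumed event rates, and at their largest on no late event being judged related. They show the direction and possible scale and do not predict this trial.

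**What to change.** 1. Delete the 8.2 sentence or align it, so that one rule holds across 8.2, 8.3.4 and 8.3.7: all SAEs and all AEs of grade 3 or higher are recorded to Day 90 regardless of relatedness. Expedited reporting can keep its own criteria.
2. In 10.1.8.1 and 9.4.2, make clear that database entry and listings cover all recorded events under that rule, and state how the 8.3.6 exemption fits with it.
3. In 9.4.2 and 9.4.6, state that the primary safety endpoint counts events over the 10-day intervention period, as in the objective. Report the count to Day 90 as a secondary safety analysis.

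The cost is wording. Section 8.3.4 already requires these data and the visits are already scheduled. The change is best made before follow-up visits accumulate, because events not recorded at Day 30 or Day 90 may be hard to recover.

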8.3 ADVERSE EVENTS AND SERIOUS ADVERSE EVENTS

8.3.1 DEFINITION OF ADVERSE EVENTS (AE)

Adverse event means any untoward medical occurrence associated with the use of an intervention in humans, (which may cause worsening of a pre-existing medical condition), whether or not it is considered intervention-related [FDA (21 CFR 312.32 (a))].

Any medical condition that is present at the time participant provided consent to the protocol will be considered as baseline and not reported as an AE. However, if the severity of any pre-existing medical condition increases after consenting, it will be recorded as an AE.

Given the nature of severity and unpredictable clinical course and outcomes of the underlying illness, participants will have many symptoms and abnormalities in health or vital status and laboratory findings. All Grade 3 and 4 AEs will be captured as AEs in this trial. These grades are according to the CTCAE (Common Terminology Criteria for Adverse Events, Version 5.0, November 27, 2017. U.S. Department of Health and Human Services, National Institutes of Health).

8.3.2 DEFINITION OF SERIOUS ADVERSE EVENTS (SAE)

An SAE is defined as "An AE or suspected adverse reaction is considered serious if, in the view of either the investigator or the sponsor, it results in any of the following outcomes:

- A life-threatening AE;
- New hospitalization or prolongation of existing hospitalization;
- A persistent or significant incapacity or substantial disruption of the ability to conduct normal life functions,
- Death,
- Any other event requiring medical or surgical treatment to prevent one of the outcomes above

All SAEs, as with any AE, will be assessed for severity and relationship to study intervention. All SAEs will be recorded on the appropriate SAE eCRF. All SAEs will be followed through resolution or stabilization by a licensed study physician (for IND studies, a physician listed on the Form FDA 1572 as the site PI or Sub-Investigator).

In this protocol, other safety events will be defined as follows:

Suspected Unexpected Serious Adverse Reaction (SUSAR): An adverse reaction that is both unexpected (not consistent with risks outlined in the study protocol), serious, and meets the definition of a suspected adverse reaction. A Serious Unexpected Serious Adverse Reactions (SUSAR) is any SAE where a causal relationship with the study product NR is at least reasonably possible but has not been documented in currently available published reports or data. In making this assessment, there should be consideration of the probability of an alternative cause (for example, COVID-19 itself or some other pre-existing conditions or comorbidities preceding randomization), the timing of the event with respect to study treatment and the response to withdrawal of the study treatment.

8.3.3 CLASSIFICATION OF AN ADVERSE EVENT

8.3.3.1 SEVERITY OF EVENT

In the protocol, the following guidelines will be used to describe severity of adverse events:

- Mild (Grade 1): Events require minimal or no treatment and do not interfere with the participant's daily activities.
- Moderate (Grade 2): Events result in a low level of inconvenience or concern with the therapeutic measures. Moderate events may cause some interference with functioning.
- Severe (Grade 3): Events interrupt a participant's usual daily activity and may require systemic drug therapy or other treatment. Severe events are usually potentially life-threatening or incapacitating. Of note, the term "severe" does not necessarily equate to "serious".
- Severe (Grade 4): Events that are potentially life threatening.
- Death (Grade 5)

8.3.3.2 RELATIONSHIP TO STUDY INTERVENTION

Study investigators will grade the strength of the relationship of an adverse event to study drug or study procedures as follows:

- Definitely Related: The event follows: a) A reasonable, temporal sequence from a study procedure; and b) Cannot be explained by the known characteristics of the participant's clinical state or other therapies; and c) Evaluation of the participants' clinical state indicates to the investigator that the experience is definitely related to study procedures.
- Probably or Possibly Related: The event should be assessed following the same criteria for "Definitely Associated". If in the investigator's opinion at least one or more of the criteria are not present, then "probably" or "possibly" associated should be selected.
- Probably Not Related: The event occurred while the participant was on the study but can reasonably be explained by the known characteristics of the participant's clinical state or other therapies.
- Definitely Not Related: The event is definitely produced by the participant's clinical state or by other modes of therapy administered to the participant.
- Uncertain Relationship: The event does not meet any of the criteria previously outlined.

8.3.3.3 EXPECTEDNESS

The study investigators will be responsible for determining whether an AE is expected or unexpected. An AE will be considered unexpected if the nature, severity, or frequency of the event is not consistent with the risk information previously described for the study intervention and hospital course.

